8.2 Secondary Objectives

- To compare objective response rate (ORR) by IIR using RECIST 1.1 of subjects treated with lenvatinib in combination with everolimus or pembrolizumab versus sunitinib.
- To compare overall survival (OS) of subjects treated with lenvatinib in combination with everolimus or pembrolizumab versus sunitinib.
- To compare safety and tolerability of treatment with lenvatinib in combination with everolimus or pembrolizumab versus sunitinib, including the assessment of the proportion of subjects who discontinued treatment due to toxicity and time to treatment failure due to toxicity.
- To compare the impact of treatment on Health-Related Quality of Life (HRQoL) as assessed by using the Functional Assessment of Cancer Therapy Kidney Index-Disease-Related Symptoms (FKSI-DRS), the European Organization for the Research and Treatment of Cancer (EORTC) QLQ-30 and the European Quality of Life (EuroQOL) EQ-5D-3L instruments, for subjects treated with lenvatinib in combination with everolimus or pembrolizumab versus sunitinib.
- To assess PFS on next-line of therapy (PFS2) as reported by investigator.
- To assess PFS based on investigator assessment per RECIST v.1.1.
- To characterize the population pharmacokinetics (PK) of lenvatinib when co-administered with everolimus or pembrolizumab.
- To compare the PK of pembrolizumab from this study to historical data.
- To characterize the population PK of everolimus when co-administered with lenvatinib.
- To assess the PK/pharmacodynamic relationship between exposure and efficacy/biomarkers/safety, if possible, using a mechanistic approach.

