9.7.1.8.2 ADVERSE EVENTS

Adverse events will be graded using CTCAE v4.03. The AE verbatim descriptions (investigator terms from the CRF) will be classified into standardized medical terminology using the Medical Dictionary for Regulatory Activities (MedDRA). Adverse events will be

coded to the MedDRA lower level term (LLT) closest to the verbatim term. The linked MedDRA preferred term (PT) and primary system organ class (SOC) are also captured in the database.

A TEAE is defined as an AE that emerges during treatment, having been absent at pretreatment (Baseline) or

- Reemerges during treatment, having been present at pretreatment (Baseline) but stopped before treatment, or
- Worsens in severity during treatment relative to the pretreatment state, when the AE is continuous.

Only those AEs that are treatment-emergent will be included in summary tables. All AEs, treatment-emergent or otherwise, will be presented in subject data listings.

The TEAEs will be summarized by treatment arm. The incidence of TEAEs will be reported as the number (percentage) of subjects with TEAEs by SOC and PT. A subject will be counted only once within an SOC and PT, even if the subject experienced more than 1 TEAE within a specific SOC and PT. The number (percentage) of subjects with TEAEs will also be summarized by maximum severity (highest CTCAE grade).

The number (percentage) of subjects with treatment-related TEAEs will be summarized by SOC and PT. Treatment-related TEAEs include TEAEs that were considered by the Investigator to be possibly or probably related to study drug or TEAEs with a missing causality. The number (percentage) of subjects with treatment-related TEAEs will also be summarized by maximum severity (by highest CTCAE grade).

The proportion of subjects who discontinue treatment due to toxicity will be summarized by frequency counts and percentages. Median, upper and lower quartiles of time to treatment failure due to toxicity will be summarized for subjects who discontinue study treatment due to TEAEs.

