##### 3.1.2 Secondary Objectives

The secondary objectives of this study are:

- To compare ORR by IIR using RECIST 1.1 of subjects treated with lenvatinib in combination with everolimus or pembrolizumab versus sunitinib.
- To compare overall survival (OS) of subjects treated with lenvatinib in combination with everolimus or pembrolizumab versus sunitinib.
- To compare safety and tolerability of treatment with lenvatinib in combination with everolimus or pembrolizumab versus sunitinib, including the assessment of the proportion of subjects who discontinued treatment due to toxicity and time to treatment failure due to toxicity.
- To compare the impact of treatment on HRQoL as assessed by using the Functional Assessment of Cancer Therapy Kidney Syndrome Index-Disease-Related Symptoms (FKSI-DRS), the European Organization for the Research and Treatment of Cancer (EORTC) QLQ-30 and the EuroQol EQ-5D-3L instruments, for subjects treated with lenvatinib in combination with everolimus or pembrolizumab versus sunitinib.
- To assess PFS on next-line of therapy (PFS2) as reported by investigator.
- To assess PFS based on investigator assessment per RECIST 1.1.
- To characterize the population pharmacokinetics (PK) of lenvatinib when co-administered with everolimus or pembrolizumab.

- To compare the PK of pembrolizumab from this study to historical data.
- To characterize the population PK of everolimus when co-administered with lenvatinib.
- To assess the PK/pharmacodynamic relationship between exposure and efficacy/ biomarkers/ safety, if possible, using a mechanistic approach.

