### 5.6.1 Extent of Exposure

#### 5.6.1.1 Study Treatment Extent of Exposure

Duration of treatment for study medications individually and/or in combination (overall) will be summarized with descriptive statistics. The dosing end date will be imputed to the analysis cutoff date if the subject is still on treatment at the time of the data cutoff, and the dose will be imputed with the last dose recorded in the database for that subject.

The duration of individual study drug in months will be  $(\text{Date of the last dose} - \text{Date of the first dose} + 1) / 30.4375$ , including drug interruption days. For overall treatment duration, it is defined as the duration between the earliest first dose start date of study drugs and the latest last dose end date of study drugs.

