Dose reduction could be applied to lenvatinib (either 20mg/day or 18mg/day reduce to 14, 10, and 8 mg/day), everolimus (5 mg every day reduce to 5 mg every other day), and sunitinib (50 mg/day reduce to 37.5, 25 mg/day of schedule 4/2). Dose interruption could apply to all study drugs. Definition of dose interruption only includes the scenario that the before and after dose 0 (interruption period), the dose levels or dosing frequency are the same. For example: 20 mg lenvatinib followed by 0 mg and followed by 20 mg lenvatinib; 5 mg everolimus every day followed by 0 mg followed by 5 mg everolimus every day. If dose level reduces from previous dose level after dose interruption period (dose 0), it should count into dose reduction not dose interruption. For example: (1) 20 mg/day lenvatinib followed by 0 mg followed by 14 mg/day lenvatinib; (2) 5 mg everolimus every day followed by 0 mg followed by 5 mg everolimus every other day; the period with 0 mg should not count into dose interruption instead should count as dose reduction. If after dose 0 mg, the subject discontinued from treatment permanently, it should count as treatment discontinuation instead of dose interruption.

Number of subjects with dose reductions and dose interruptions of lenvatinib, everolimus, sunitinib, and pembrolizumab (dose reduction not applied to pembrolizumab) will be summarized by frequency counts and percentages according to study medication data.

Time to first dose reduction is defined as the date of the first dose to the date of first dose reduction, or the date of first dose interruption if subjects had dose interruption followed by dose reduction. There will be two ways to estimate the time to dose reduction. (1) Only include the subjects who had dose reduction events. Descriptive statistics will be generated to describe the time to first dose reduction for these patients. (2) Include all subjects. For subjects who did not have dose reduction, it will be censored at the date of last dose. For this summary, Kaplan-Meier method will be used to estimate the median time to first dose reduction for all the subjects by the treatment arms.

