### 5.6.2 Adverse Events

The AE verbatim descriptions (investigator terms from the CRF) will be classified into standardized medical terminology using the Medical Dictionary for Regulatory Activities (MedDRA). Adverse events will be coded to the MedDRA (Version 21.1 or higher) lower level term (LLT) closest to the verbatim term. The linked MedDRA preferred term (PT) and primary system organ class (SOC) will also be captured in the database. The Common Terminology Criteria for Adverse Events (CTCAE) version 4.03 will be used to assess the severity of AEs.

A treatment-emergent adverse event (TEAE) is defined as an AE that emerged during treatment (up to 30 days after the subject's last dose of study drug), having been absent at pretreatment (Baseline) or

- Reemerged during treatment or up to 30 days following last dose of study drug, having been present at pretreatment (Baseline) but stopped before treatment, or
- Worsened in severity during treatment or up to 30 days following last dose of study drug relative to the pretreatment state, when the AE was continuous.

The serious AE that emerged up to 120 days after the subject's last dose of study drug is also counted as TEAE.

Only those AEs that are treatment emergent will be included in summary tables. All AEs, treatment emergent or otherwise, will be presented in subject data listings.

An overview table, including the incidence of and the number of subjects with TEAEs, TEAEs with grade 3 or above, serious adverse events (SAEs), deaths, and TEAEs that led to treatment discontinuation (discontinuation of both agents in arm A or B), dose reduction, or dose interruption will be provided by treatment arms.

The TEAEs will be summarized by treatment groups. The incidence of TEAEs will be reported as the number (percentage) of subjects with TEAEs by SOC and PT. A subject will be counted only once within a SOC and PT, even if the subject experienced more than 1 TEAE within a specific SOC and PT. The number (percentage) of subjects with TEAEs will also be summarized by maximum severity.

The number (percentage) of subjects with TEAEs will also be summarized by relationship to study drug. Summaries of TEAE incidence rate adjusted by treatment duration will be presented.

In summary, the following TEAE tables will be provided:

- Overview of TEAE and treatment-related TEAE
- TEAE by SOC and PT (Any Grade and Grade  $\geq 3$ , maximum grade 3, 4 and 5)
- TEAE by decreasing frequency of PT

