- TEAE with each PT frequency  $\geq 5\%$  by PT
- TEAE by SOC, PT and Worst Grade of Toxicity
- Treatment-related TEAE by SOC and PT (Any Grade and Grade  $\geq 3$ )
- Exposure-adjusted TEAEs

The following subject AE listings (treatment emergent or otherwise) will be provided:

- All AEs
- All AEs with CTCAE Grade 3 or above

The proportion of subjects who discontinue treatment due to toxicity will be summarized by frequency counts and percentages. Median, upper and lower quartiles of time to treatment failure (discontinuation of both agents in arm A or B) due to toxicity will be summarized for subjects who discontinue study treatment due to TEAEs.

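### Minor, cheap improvement: time to treatment failure due to toxicity is summarized only among those who stopped for TEAEs, so its median is hard to interpret alone; add an all-treated-subjects time course

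*SAP*

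**What the plan says.** Protocol 8.2 and SAP 3.1.2 share a secondary objective: "To compare safety and tolerability of treatment with lenvatinib in combination with everolimus or pembrolizumab versus sunitinib". Within it they name, for assessment, the proportion of subjects who "discontinued treatment due to toxicity and time to treatment failure due to toxicity".

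Two summaries follow in SAP 5.6.2. The first covers the proportion: "The proportion of subjects who discontinue treatment due to toxicity will be summarized by frequency counts and percentages". The second covers the time and is restricted to subjects who stopped: median and quartiles of time to treatment failure "due to toxicity will be summarized for subjects who discontinue study treatment due to TEAEs". Protocol 9.7.1.8.2 has the same restriction: "Median, upper and lower quartiles of time to treatment failure due to toxicity will be summarized", again only for those who stopped for TEAEs. The SAP adds that failure in Arms A and B means stopping both agents. Neither document gives this endpoint a censoring rule, an all-subject estimate or a test.

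Nearby analyses bear on the point:

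- SAP 5.6.1.3 summarizes time to first dose reduction in two ways. One uses only subjects with a reduction. In the other, "Kaplan-Meier method will be used to estimate the median time to first dose reduction for all the subjects", with subjects who had no reduction censored at last dose.
- SAP 5.6.1.1: "Duration of treatment for study medications individually and/or in combination (overall) will be summarized with descriptive statistics".
- SAP 5.6.2: "Summaries of TEAE incidence rate adjusted by treatment duration will be presented". The listed exposure-adjusted tables are for TEAEs and SAEs, not for discontinuation due to TEAE.
- SAP 5.2.2 and protocol 9.7.1.3 tabulate reasons for stopping study drug by arm.

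The clock starts at randomization in SAP 5.1.2 and at first dose in protocol 9.7.1.1.2.

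**The concern.** A subject enters the event-only median only if toxicity ends treatment before progression, another reason or the data cutoff does. Where subjects leave sooner for other reasons, late toxicity stops are removed and the surviving ones look early. The trial is designed on the expectation that progression comes sooner on sunitinib, so the event-only medians should differ even if the toxicity-stop hazards are the same. What is at stake is how the tolerability comparison with sunitinib is read. No efficacy conclusion depends on it.

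**Working it through.** The documents state no figure for this endpoint, so there is none to reproduce. The check is an illustration under stated assumptions.

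**Inputs from SAP section 4.** Median PFS 12.3 months on sunitinib; hazard ratio 0.714; about 350 subjects per arm; 34 months of enrollment; final PFS analysis at about month 45.

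**Assumptions.** Toxicity-stop hazard h constant, equal in all arms, at 0.01, 0.02 or 0.03 per month. Planned PFS stands in for all other stops. Uniform entry, so potential follow-up is uniform on 45 − 34 = 11 to 45 months.

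**Step 1, other-stop hazards.** Sunitinib: ln 2 / 12.3 = 0.0564 per month. Combination: 0.714 × 0.0564 = 0.0402 per month.

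**Step 2, event-only median.** With g the other-stop hazard, the density of an observed toxicity stop at time s is h · exp(−(h + g)s) · P(follow-up ≥ s). Its integral is the proportion stopping for toxicity; the median splits that integral in half. Without a cutoff the median would be ln 2 / (h + g), which shows directly that it depends on g as well as h.

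**Step 3, standard error.** SE of each median = 1 / (2 f √n), with f the density at the median among those who stopped and n the expected number of toxicity stops.

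| h per month | Median, sunitinib | Median, combination | Gap | SE of difference | Gap / SE | Proportion stopping, sunitinib vs combination |
|---|---|---|---|---|---|---|
| 0.01 | 7.81 | 8.95 | 1.14 | 2.23 | 0.51 | 12% vs 14% |
| 0.02 | 7.20 | 8.22 | 1.01 | 1.56 | 0.65 | 22% vs 26% |
| 0.03 | 6.67 | 7.57 | 0.90 | 1.25 | 0.72 | 30% vs 35% |

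In 4,000 simulated trials per row, sunitinib had the earlier event-only median in 70%, 74% and 77%. The difference in 12-month all-subject Kaplan-Meier estimates took either sign about half the time, as it should with equal hazards.

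**Step 4, could a real excess hide?** The medians tie when h + g is the same in both arms. The combination hazard is then h + 0.0564 − 0.0402, which is 2.6, 1.8 or 1.5 times the sunitinib hazard. The proportions stopping for toxicity at those points are 12% vs 32%, 22% vs 40% and 30% vs 47%. The companion summary would show the excess.

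**Step 5, sensitivity of the gap.**

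- Front-loaded Weibull hazard with the same 12-month cumulative hazard: 0.7 to 0.9 months (shape 0.7; 0.43 to 0.63 SE) or 0.5 to 0.6 months (shape 0.5; 0.36 to 0.53 SE).
- Other-stop hazards scaled so that mean treatment duration over the three arms equals the protocol's 15 months: 0.8 to 1.2 months (no cutoff) or 0.5 to 1.0 (observed to month 45).
- Cutoff at month 38: 0.7 to 0.8 months.

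**The case against.** The summary is descriptive and names its own denominator in both documents. It has no confidence interval, test or decision rule, and the objective speaks of assessing this endpoint within a broader comparison. As a statement of when stops occurred among those who stopped, it is correct. All of that stands.

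Most of the context is also planned. The proportion stopping for toxicity sits in the same paragraph. Reasons for discontinuation by arm show the competing stops directly. With mean treatment duration, a reader can form a crude rate, count / (N × mean duration). This recovers equal rates under constant hazards and differs by only 4 to 8% between arms under the front-loaded ones. That stands too, but a crude rate says nothing about timing, which is what this endpoint is meant to describe. The proportion also differs under equal hazards, in the opposite direction to the median, so the two can give mixed signals.

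The size rests on assumed hazards. PFS is a rough proxy, because treatment beyond progression is allowed and failure in Arms A and B requires stopping two agents. In every case with a computed SE, the gap is below one SE.

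A reader might infer that the plan makes an invalid between-arm comparison, or that it would conceal a toxicity excess. The documents support neither. No comparison of these medians is specified, and step 4 shows that the planned proportions would reveal a large excess.

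Table and figure shells are in a separate document, so an all-subject display may exist there; the SAP text does not call for one.

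**Conclusion.** The point holds as a minor, optional improvement. The event-only median mixes toxicity with other stops and follow-up, and no planned analysis in the SAP gives the time course of toxicity stops over all treated subjects. Under equal assumed hazards the expected artefact is 0.9 to 1.1 months, or 0.5 to 1.2 across the sensitivity cases. If competing stops and follow-up were equal between arms, it would vanish. Only the reading of a descriptive tolerability summary is affected.

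The difference in clock start is a separate editorial matter, worth about 0 to 1 day for subjects dosed on schedule. A reader might take it as adding weight to the main point; it does not.

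**What to change.** In SAP 5.6.2, keep the event-only quartiles as descriptive. Add, by arm in the Safety Analysis Set, a Kaplan-Meier estimate of time to discontinuation due to TEAE, censoring at last dose for subjects who stop for other reasons and at data cutoff for those still on treatment. This extends the approach of SAP 5.6.1.3. Beside it show the cumulative incidence, with other discontinuations and death as competing events.

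The two answer different questions. Kaplan-Meier removes the competing hazard but reads as a probability only if toxicity stops are independent of other stops. Cumulative incidence is the observed risk but still depends on the competing hazard: with h = 0.01 in both arms it is 8.3% vs 9.0% at 12 months. Doubling the combination hazard makes it 8.3% vs 17.1%. Read both with the table of reasons for discontinuation.

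The cost is one extra table or figure. Dates and reasons for stopping are already collected, and no test, alpha or decision rule changes. Separately, state one start of the clock in SAP 5.1.2 and protocol 9.7.1.1.2.

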### 5.6.2.1 Deaths, Serious and Other Significant Adverse Events

The number (percentage) of subjects with TEAEs leading to death will be summarized by MedDRA SOC and PT for each treatment group. A subject data listing of all AEs leading to death will be provided.

The number (percentage) of subjects with treatment-emergent serious adverse events (SAEs) was summarized by MedDRA SOC and PT for each treatment group. A subject data listing of all SAEs was provided.

The number (percentage) of subjects with TEAEs leading to discontinuation from study drug will be summarized by MedDRA SOC and PT for each treatment group. A subject data listing of all AEs leading to discontinuation from study drug will be provided. The number (percentage) of subjects with TEAE leading to study drug dose reduction or interruption will also be summarized by MedDRA SOC and PT for each treatment group. A subject data listing of all AEs leading to study drug dose reduction or interruption will be provided.

In summary, the following TEAE tables will be provided:

- TEAE leading to death by SOC and PT
- SAEs by SOC and PT
- Treatment-related SAEs by SOC and PT
- SAEs by decreasing frequency of PT
- Nonfatal SAEs by decreasing frequency of PT
- Exposure-adjusted SAEs
- TEAE leading to drug discontinuation by SOC and PT
- TEAE leading to drug discontinuation of Lenvatinib by SOC and PT
- TEAE leading to drug discontinuation of Everolimus/Pembrolizumab by SOC and PT
- TEAE leading to drug reduction and/or interruptions by SOC and PT
- TEAE leading to drug reduction and/or interruptions of Lenvatinib by SOC and PT
- TEAE leading to drug reduction and/or interruptions Everolimus/Pembrolizumab by SOC and PT

The following subject AE listings (treatment-emergent or otherwise) will be provided:

- All AEs with fatal outcome
- All SAEs
- All AE leading to study drug discontinuation
- All AEs leading to study drug dose reduction and/or interruption

### 5.6.2.2 Treatment-Emergent Adverse Events of Clinical Interest

Clinically significant TEAEs (CSAE) for Lenvatinib, TEAEs of special interest (AEOSI) for everolimus, pembrolizumab, respectively, will be identified based on the review of safety data by Clinical and Pharmacovigilance.

CSAE and AEOSI will be summarized by the grouped terms for any Grade and Grade  $\geq 3$ . Time to onset of the CSAE and AEOSI will be summarized using descriptive statistics for subjects with CSAE and AEOSI reported, median time to first onset, proportion of subjects with CSAE and AEOSI leading to drug withdrawal or dose modifications will be summarized for any Grade and Grade  $\geq 3$  CSAE and AEOSI. Time to onset of the CSAE and AEOSI is defined as the time from first dose to the first onset of the CSAE and AEOSI.

### 5.6.3 Laboratory Values

Laboratory results will be summarized using Système International (SI) units, as appropriate. Laboratory values that are non-missing and reported as ‘below the detectable limit’ of an assay will be replaced by half the detectable limit in the summary tables. On treatment laboratory tests will be defined as laboratory tests conducted from the start of treatment to no more than 30 days after the last dose of study treatment. Central laboratory test results will be primary data source for laboratory analyses. Only when the central laboratory tests results are missing, the local laboratory test results will be used as substitute. Other laboratory parameters collected for some individual subjects will be presented in listing only. Box and Whisker plots will also be generated for individual laboratory parameters and change from baseline by visit for all visits with at least 10% of subjects in all treatment arms.

For all quantitative parameters listed in protocol Section 9.5.1.4 Safety Assessments (Laboratory Measurements), the actual value and the change from baseline to each postbaseline visit and to the end of treatment (defined as the last on-treatment value) will be summarized by visit and treatment group using descriptive statistics. Qualitative parameters listed in protocol Section 9.5.1.4 will be summarized using frequencies (number and percentage of subjects), and changes from baseline to each postbaseline visit and to end of treatment will be reported using shift tables. Percentages will be based on the number of subjects with both nonmissing baseline and relevant postbaseline results.

